9.4.2.1. Primary Endpoint(s)

The difference in area under the log₁₀-transformed DENV RNA viral load curves from immediately prior to first dose (baseline) until Day 5 for JNJ-64281802 versus placebo dosing will be derived from a mixed model with treatment regimen and the stratification factors as fixed factors and baseline log₁₀ viral load as a covariate, calculating least square mean differences, including the 90% 2-sided confidence intervals in the ITT-I population with a primary dengue infection based on IgG profile.

9.4.2.2. Secondary Endpoint(s)

Descriptive statistics and mean (and standard error) graphs will be shown for the log₁₀ DENV RNA and viremia actual values and changes from baseline over time in participants with primary DENV infection.

In participants with primary DENV infection, the proportion of participants within the DENV RNA and viremia categories (\geq lower limit of quantification [LLOQ], $<$ LLOQ target detected and, $<$ limit of detection [LOD] target not detected) will be shown in a frequency tabulation per analysis time point.

Time to undetectable DENV RNA/viremia will be analysed using Kaplan-Meier estimates analysis. A summary table including number of participants with primary DENV infection included in the analysis, number of participants censored, 25th and 75th percentiles and median time-to event, with 95% confidence intervals based on log-log transformation method, will be presented. The data will be presented graphically using the Kaplan-Meier estimate of the survival function by treatment.

Descriptive statistics will also be used to describe the IgM and IgG response. The proportion of participants with antibody positivity and the titer and timing of the antibody response will be determined. Descriptive statistics will include sample size, mean, standard deviation, coefficient of variation, geometric mean, median, minimum, and maximum.

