| Blood sample collection for pharmacokinetics (CCI formulation) | | | ● | X | X | ● | | ● | X | X | ● | | ● | ● | ● | X | X | X | X | X | X | X | X |

| Phase | Pre-screening (optional) | Screening/Baseline ^a | Double-blind Treatment ^b | | | | | | | | | | | | | | | Follow-Up ^b | | | Early Exit Visit ^b |
|---|--------------------------|---------------------------------|--|--|--|---|--|---|----------------|----------------|----------------|----------------|---|---|---|----|----|------------------------|---|---|-------------------------------|
| | | | During inpatient stay (or ambulatory visits ^y) | | | | | | | | | | | | Extended stay at inpatient facility (for participants with dengue warning symptoms) | | | During on Site Visits | | | |
| Day | | 0 ^a | 1 ^a | | | 2 | | | 3 ^y | 4 ^y | 5 ^y | 6 ^y | 7 | 8 | 9 | 14 | 21 | 28 | | | |
| Month | | | | | | | | | | | | | | | | | | | | 6 | |
| CCI | | | | | | | | | | | | | | | | | | | | | |
| Blood sample collection for plasma protein binding ^f | | | ● | | | | | | | | | X | | | X | | | | | | |
| Blood sample collection for alpha 1 acid glycoprotein ^f | | | ● | | | | | | | | | X | | | X | | | | | | |
| Antiviral activity Assessments | | | | | | | | | | | | | | | | | | | | | |
| Blood sample collection for viral load determination (DENV RNA, infectious virus and NS1) | | X | | | | X | | ● | | | X | X | X | X | X | X | X | X | X | X | X |
| Immune/Viral sequencing Assessments | | | | | | | | | | | | | | | | | | | | | |
| Blood sample collection for humoral immunity (IgG, IgM and nAb) | | X | | | | | | ● | | | | X | X | X | X | X | X | X | X | X | X |

[figure not shown]

| Phase | Pre-screening (optional) | Screening/Baseline ^a | Double-blind Treatment ^b | | | | | | | | | | | | | | | Follow-Up ^b | | | Early Exit Visit ^b |
|---|--------------------------|---------------------------------|--|--|---|---|---|--|----------------|----------------|----------------|----------------|---|---|---|----|----|------------------------|----------------|---|-------------------------------|
| | | | During inpatient stay (or ambulatory visits ^y) | | | | | | | | | | | | Extended stay at inpatient facility (for participants with dengue warning symptoms) | | | During on Site Visits | | | |
| Day | | 0 ^a | 1 ^a | | | 2 | | | 3 ^y | 4 ^y | 5 ^y | 6 ^y | 7 | 8 | 9 | 14 | 21 | 28 | | | |
| Month | | | | | | | | | | | | | | | | | | | | 6 | |
| CCI | | | | | | | | | | | | | | | | | | | | | |

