3. OBJECTIVES AND ENDPOINTS

| Objectives | Endpoints |
|---|---|
| Primary | |
| 
 • Investigate the antiviral activity of JNJ-64281802 versus placebo in terms of reduction of DENV RNA in primary DENV infection | 
 • Area under the log₁₀-transformed DENV RNA viral load (log₁₀ VL) curve from baseline until Day 5 (AUC_{D1-D5} [log₁₀VL]). |

| Objectives | Endpoints |
|---|---|
| Secondary | |
| 
 Assess the safety and tolerability of JNJ-64281802 in primary and secondary DENV infection | 
 AEs ECGs physical examinations vital signs clinical laboratory assessments |
| 
 Investigate the antiviral activity of JNJ-64281802 versus placebo based on other virological endpoints in primary DENV infection | 
 Virologic endpoints derived from the DENV RNA, including 
 Occurrence of detectable DENV RNA at each time point in primary DENV infection Time to undetectable DENV RNA in primary DENV infection |
| 
 Evaluate the PK of JNJ-64281802 | 
 PK parameters for JNJ-64281802 |
| Exploratory | |
| 
 Investigate the antiviral activity of JNJ-64281802 versus placebo based on DENV infectious viral titer (further referred to as viremia) in primary DENV infection | 
 Virologic endpoints derived from viremia, including 
 Area under the log₁₀-transformed viremia curve from baseline until Day 5 in primary DENV infection Occurrence of detectable viremia at each timepoint in primary DENV infection Time to undetectable viremia in primary DENV infection |
| 
 To explore the relationship between the exposure and antiviral activity of JNJ-64281802 | 
 PK (plasma concentrations or exposure parameters) of JNJ-64281802. Area under the log₁₀-transformed viremia or DENV RNA viral load. |

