JNJ-64281802 (in either CCI formulation) or matching placebo will be administered according to the following dosing regimens:

CCI

The CCI formulation will be introduced for use in newly recruited participants, when it becomes locally available.

CCI

CCI

When dosed in fasted condition in 16 healthy volunteers, the JNJ-64281802 C_{\max} and AUC_{∞} were similar between CCI and CCI, with geometric mean ratios of 1.06 and 1.00, respectively. CCI

When administered with a standardized breakfast, JNJ-64281802 C_{\max} was increased by 33, 76, and 178% compared to fasted conditions for a single dose of 50, 200 and 800 mg, respectively. For AUC_{∞} this increase was 12, 69, and 143%, respectively.

CCI

The participants will be discharged from the inpatient facility on Day 6 (on Day for ambulatory visits) after the assessments indicated in the [Schedule of Activities](#) have taken place and given their clinical status is satisfactory for discharge in the opinion of the investigator. Participants who develop dengue warning symptoms as defined by WHO⁰ will remain at the inpatient facility after Study Day 6 for an additional 3 days and planned outpatient assessments will be performed by the study team members, where required. Patients with severe dengue (DHF or DSS), or participants who are hemodynamically unstable or require interventions, can be transferred to a hospital at any time during the inpatient stay, at the investigator's discretion. Participants with severe dengue or dengue warning symptoms after Study Day 9 will be moved to a hospital. After discharge, the participants will be asked to return on Days 14, 21, and 28 (± 2 days) and, thereafter, to perform remote follow-up visits every two weeks (± 4 days) till 6 months post dosing for assessments specified in the [Schedule of Activities](#). If the participant remains in the inpatient facility beyond Day 6, planned outpatient study assessments will be performed at the inpatient facility as specified in the [Schedule of Activities](#).

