c. Retrospective analysis of the screening samples will be performed.

d. Maximum 14 samples will be collected in case repeat required at D1 and in case prolongation stay at unit until Day 9.

e. Includes viral load, humoral immunity, serum proteins (including cytokines) and viral genome sequencing

f. Repeat or unscheduled samples may be taken for safety reasons or technical issues with the samples.

g. Additional 87.6 mL of blood per participant will be collected in case of an extended stay at the inpatient facility from Day 6 to Day 9.

h. At pre-screening or at screening, if not yet performed by a health care facility or practitioner as part of standard of care.

i. Volume per blood sample can be reduced from 30 mL to 10 mL at Day 28, subject to the local regulations and investigator's decision.

Note: An indwelling intravenous cannula may be used for blood sample collection.

Sample Collection and Handling

The actual dates and times of sample collection must be recorded in the CRF or laboratory requisition form. If blood samples are collected via an indwelling cannula, an appropriate amount (1 mL) of serosanguineous fluid slightly greater than the dead space volume of the lock will be removed from the cannula and discarded before each blood sample is taken. After blood sample collection, the cannula will be flushed with 0.9% sodium chloride, United States Pharmacopeia (USP) (or equivalent) and charged with a volume equal to the dead space volume of the lock.

Refer to the Schedule of Activities for the timing and frequency of all sample collections.

Instructions for the collection, handling, storage, and shipment of samples are found in the laboratory manual that will be provided. Collection, handling, storage, and shipment of samples must be under the specified, and where applicable, controlled temperature conditions as indicated in the laboratory manual.

Study-Specific Materials

The investigator will be provided with the following supplies:

- IB
- Pharmacy manual/study site investigational product and procedures manual
- Laboratory manual
- eDC Manual
- eSource Manual
- Sample ICF

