9.2. Sample Size Determination

The study will recruit in total 150 participants, with the primary objective of investigating the antiviral activity of JNJ-64281802 versus placebo based on DENV RNA in primary DENV infection and with an objective to describe the safety and tolerability of JNJ-64281802 in participants with DENV infection. The sample size can be revised after an interim analysis on the proportion of primary versus secondary DENV infections (refer to Section 9.5, Interim Analysis).

For the objective of antiviral activity in participants with a primary DENV infection, the hypothesis is that the intervention effect is superior to placebo as measured on the DENV RNA log₁₀ viral load curve from baseline on Day 1 until Day 5.

To assess sample size requirements for this hypothesis, data of 47 DENV RNA curves were estimated similar to the DENV RNA curves graphically presented in the balapiravir trial. All curves were considered as balapiravir did not have an effect on the viral load. A limit of detection of 2.3 log copies/mL was assumed. Although the majority of the population included in the balapiravir trial suffered from a secondary infection⁰, these estimated DENV RNA curves were considered representative for a primary infected dengue population. As the clearance of DENV RNA occurs earlier and faster in patients with secondary dengue, this is a conservative assumption.⁰

The 47 estimated DENV RNA curves were used to calculate the means, standard deviations and correlations of the log₁₀ viral loads over time. These calculated values were thereafter used to simulate 10,000 trials, each with a sample size of 80 participants. A treatment effect of 0.30 log₁₀ copies/mL per day DENV RNA clearance on top of placebo, or two-fold reduction of the viral load was applied. Based on these 10,000 simulated trials and using a general linear model with treatment regimen as fixed factor and baseline log₁₀ viral load as a covariate, a sample size of 80 participants (40 per group) was estimated to provide a power of at least 80% at the one-sided 5% significance level to detect an intervention effect of 0.30 log₁₀ copies/day additional DENV RNA clearance when compared to placebo.

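### After Day 6, time to undetectable RNA is read daily only in participants kept in for warning symptoms, so the planned Kaplan-Meier curve can partly reflect clinical course

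*Protocol*

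**What the plan says.** Protocol 9.4.2.2 gives the method for this secondary endpoint: "Time to undetectable DENV RNA/viremia will be analysed using Kaplan-Meier estimates analysis". The outputs are the quartiles with 95% confidence intervals, and "The data will be presented graphically using the Kaplan-Meier estimate of the survival function by treatment". The section does not define the event date, the censoring rule or the handling of unequal visits, and it plans no between-arm test. Protocol 3 lists a companion endpoint, "Occurrence of detectable DENV RNA at each time point in primary DENV infection", which 9.4.2.2 tabulates by time point.

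The Schedule of Activities (1.3) places Days 7, 8 and 9 under "Extended stay at inpatient facility (for participants with dengue warning symptoms". The row "Blood sample collection for viral load determination (DENV RNA, infectious virus and NS1" is marked there. Protocol 4.1 gives the trigger: participants who develop warning symptoms "will remain at the inpatient facility after Study Day 6 for an additional 3 days". All others return on Days 14, 21 and 28 (± 2 days). Footnote d to Table 1 in Section 8 says: "Maximum 14 samples will be collected in case repeat required at D1 and in case prolongation stay at unit until Day 9".

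The SAP was written after early termination with five participants. Its Section 5.3 removes all efficacy analysis beyond individual profiles and plots, and 5.1.2 uses actual dates and times.

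**The concern.** Whether a participant has a reading on Days 7 to 9 depends on a clinical event after randomisation that the drug might change. Take two participants who are still detectable on Day 6 and both clear on Day 7. With warning symptoms the recorded time is Day 7; without them it is Day 14. Ordinary Kaplan-Meier treats both dates as exact.

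If the arms differ in how often warning symptoms occur, or in how those symptoms relate to late clearance, part of the separation between the curves after Day 6 comes from the visit schedule. A drug that prevents warning symptoms would have fewer Day 7 to 9 readings and would look slower to clear RNA. In the detectability table, the Day 7, 8 and 9 rows compare only a subgroup selected after randomisation.

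Clearance after Day 6 is plausible in the endpoint population, which is primary infection. Protocol 9.2 reasons: "As the clearance of DENV RNA occurs earlier and faster in patients with secondary dengue". The sample-size curves assumed a detection limit of 2.3 log copies/mL, while SAP 5.3 lists limits of 1.46 to 1.78 log10 copies/mL. With a lower limit, target-not-detected results come later. Neither document says what share is still detectable on Day 6.

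**Working it through.** **Step 1. Is RNA really drawn on Days 7 to 9?** The schedule's columns are broken in the extracted text, so I checked them against Table 1. Footnote g gives 87.6 mL of extra blood for an extended stay.
- Volumes per day: hematology 3, chemistry 8, coagulation 2.7, PK 3, shared tube including viral load 10, host RNA 2.5.
- 3 + 8 + 2.7 + 3 + 10 + 2.5 = 29.2 mL, and 3 × 29.2 = 87.6 mL, which matches exactly.
- Without the 10 mL tube, 3 × 19.2 = 57.6 mL, which does not match.
- Footnote d is consistent: 11 standard samples + 3 = 14. Because it also mentions a Day 1 repeat, it supports the reading but does not settle it alone.

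**Step 2. Shift for one participant.** Recorded time is the first scheduled sample at or after true clearance.

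| True clearance | With warning symptoms | Without | Difference |
|---|---|---|---|
| after Day 6, by Day 7 | 7 | 14 | 7 days |
| after Day 7, by Day 8 | 8 | 14 | 6 days |
| after Day 8, by Day 9 | 9 | 14 | 5 days |

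With the ± 2 day window the difference runs from 12 − 9 = 3 to 16 − 7 = 9 days. Clearance by Day 6 is recorded identically for everyone.

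**Step 3. Shift between arms.** Let w be an arm's warning-symptom rate, assumed independent of clearance time. Then the recorded share undetectable by Day 9 is P(T ≤ 6) + w × P(6 < T ≤ 9). With the same true clearance in both arms, the artefactual gap is (w₁ − w₂) × P(6 < T ≤ 9). If w₁ = w₂ the gap is zero. The documents give none of these rates, so everything below is assumption.

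*Weibull clearance, shape 2.5, 70% cleared by Day 6, P(6 < T ≤ 9) = 0.264:*
- Rates 25% and 25%: no arm difference. The mean recorded time is 6.8 days in both arms against a true 4.9.
- Rates 15% active and 35% placebo: 0.70 + 0.15 × 0.264 = 0.740 against 0.70 + 0.35 × 0.264 = 0.792; the true share is 0.964 in both. Medians are equal (Day 5). The 75th percentile is Day 14 against Day 8; the true value is 6.35 in both.
- The same rates with 85% or more cleared by Day 6: median and 75th percentile agree between arms.
- The same rates with 50% cleared by Day 6: gap 0.20 × 0.35 = 0.07. With 95% cleared: 0.20 × 0.05 = 0.01.

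*Log-normal clearance, median 6.5, log-SD 0.3, P(T ≤ 6) = 0.395, P(T ≤ 9) = 0.861, rates 10% active and 30% placebo:*
- Recorded Day 9 shares are 0.441 and 0.535.
- With true medians of 5.5 and 7.5 the shares are 65% against 72%, and 28% against 38%.

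**Step 4. Effect of one common grid.** No test is planned, so this is only a gauge. A two-sided 5% log-rank test, 42 per arm (84 ÷ 2), was simulated under no true difference.
- Planned visits, rates 25% and 25%: rejects 4.5 to 5.3%.
- Planned visits, rates 15% and 35%: 4 to 9%.
- Planned visits, rates 10% and 50%: 5 to 16%.
- Everyone on Days 1 to 6, 14, 21 and 28: 4 to 6%.

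The planned-visit ranges cover 30% to 95% cleared by Day 6; the common-grid range covers 30% to 70%.

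**The case against.** The strongest reply is that the plan states neither the event date nor the censoring rule, so taking the first undetectable sample as an exact time is an inference. Protocol 9 and 9.4 leave technical detail to the SAP, and the SAP introduction mentions a stable earlier draft that is not available here. That is fair. But ordinary Kaplan-Meier is the named method, and nothing in the protocol separates it from the unequal visits.

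Three further points stand and limit the concern. The curves are by treatment, not by warning-symptom status, so equal rates with the same link to clearance create no arm difference. Only participants still detectable on Day 6 are affected. No test hangs on the result.

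A reader might infer a large shift in the median. Under the log-normal assumptions above, the recorded medians are indeed Day 8 against Day 14, but only because the placebo share by Day 8 is 50.3%, just past one half. With true medians of 5.5 or 7.5 the recorded medians agree. The 75th-percentile jump in Step 3 also sits near a threshold (74.0% recorded by Day 9), so the Day 9 share is the steadier measure.

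**Conclusion.** The point holds as a limited flaw in the protocol's planned analysis. The conditional sampling is established by the schedule and the exact blood-volume match, and the individual shift of 5 to 7 days follows by arithmetic if the first undetectable sample is the event time. The between-arm effect is conditional. It needs warning-symptom rates, or their link with late clearance, to differ by arm, and enough participants still detectable on Day 6. For a 20-point difference in rates, the Weibull cases listed give a gap of about 1 to 7 percentage points in the Day 9 share, and the log-normal case about 9.

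A reader might conclude that the two virological secondary endpoints cannot serve their objective. The documents do not support that: detectability on Days 1 to 6, 14, 21 and 28 remains a full randomised comparison, and clearance by Day 6 is recorded alike in everyone. Nor does it touch the primary AUC, which ends at Day 5, or the reported results, because the SAP carries no Kaplan-Meier analysis. It matters for the protocol's plan and for any later trial that reuses it.

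**What to change.** In 9.4.2.2, derive time to undetectable RNA and viremia for every participant from the visits common to all: Days 1 to 6, 14, 21 and 28. State the event and censoring rules. Preferably use interval-censored estimation (Turnbull) between the last detectable and first undetectable common visit. The common grid alone already removes the dependence on clinical course, while interval censoring also avoids treating Day 14 as an exact clearance date. Interval censoring on all visits without the common grid would assume that visit timing is unrelated to clearance, which sampling triggered by warning symptoms may violate; keep it as a sensitivity analysis.

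Leave Days 7 to 9 out of the between-arm detectability table and show those values in listings.

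The cost is a change of wording and one different procedure, with no new samples. The downside is that Day 7 to 9 values do not enter the main comparison. This is a cheap improvement.

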9.4.3. Safety Analyses

All participants enrolled into the study who received at least one dose of study intervention will be included in the safety population. Participants in this population will be defined by the study intervention actually received, not by randomization assignment. The safety population will be used for all safety analyses.

Safety data will be presented descriptively. No statistical testing of safety data is planned.

Adverse Events

The verbatim terms used in the CRF by investigators to identify adverse events will be coded using the Medical Dictionary for Regulatory Activities (MedDRA). Any AE occurring at or after the initial administration of study intervention through the day of last dose plus 20 days is considered to be treatment emergent. All reported adverse events will be included in the analysis. For each

adverse event, the percentage of participants who experience at least 1 occurrence of the given event will be summarized by intervention group.

Summaries, listings, datasets, or participant narratives may be provided, as appropriate, for those participants who die, who discontinue intervention due to an adverse event, or who experience a severe or a serious adverse event.

Clinical Laboratory Tests

Laboratory data will be summarized by type of laboratory test. Reference ranges and markedly abnormal results (specified in the Statistical Analysis Plan) will be used in the summary of laboratory data. Descriptive statistics will be calculated for each laboratory analyte at baseline and for observed values and changes from baseline at each scheduled time point. Changes from baseline results will be presented in pre- versus post-intervention cross-tabulations (with classes for below, within, and above normal ranges). Frequency tabulations of the laboratory abnormalities will be made. A listing of participants with any laboratory results outside the reference ranges will be provided. A listing of participants with any markedly abnormal laboratory results will also be provided.

Electrocardiogram

The effects on cardiovascular variables will be evaluated by means of descriptive statistics and frequency tabulations. These tables will include observed values and changes from baseline values (the initial ECG will be used as baseline). Electrocardiogram data will be summarized by ECG parameter. Descriptive statistics will be calculated at baseline and for observed values and changes from baseline at each scheduled time point. Frequency tabulations of the abnormalities will be made.

Vital Signs

Vital signs including pulse/heart rate, respiratory rate, and blood pressure (systolic and diastolic) will be summarized over time, using descriptive statistics and/or graphically. The percentage of participants with values beyond clinically important limits will be summarized.

Physical Examinations

Physical examination findings will be summarized at each scheduled time point. Frequency tabulations of the abnormalities will be made.

